#### **Lesions identified on a chest x-ray should be imaged by a CT or MRI scan.**

The same method of assessment and the same technique should be used to characterize each site of disease at baseline and during follow-up evaluations.

#### **Documentation of Target and Non-Target Lesions**

All measurable or target lesions, up to a maximum of 5 lesions per organ and 10 lesions total, representative of all sites of disease, will be identified and measured at baseline and followed as target lesions throughout the study. Target lesions should be selected on the basis of their size (longest diameter) and suitability for accurate reproducibility and measurement on follow-up imaging. The SLD for all target lesions will be calculated and reported as the baseline SLD. The baseline SLD will be used as a reference by which to characterize the objective tumor response at each subsequent tumor assessment timepoint. The smallest sum of the longest diameters recorded since baseline will be used as reference when evaluating for progression. All other lesions (or sites of disease) should be identified as non-target lesions and should be recorded at baseline.

Measurement of these lesions is not required, but the presence, absence, or worsening of each should be documented throughout follow-up.

#### **Response Confirmation**

To be assigned a status of CR or PR, changes in tumor measurements must be confirmed by consecutive repeat assessments that should be performed no less than 28 days after the criteria for response are first met.

Overall time point responses for all possible combinations of responses in target and non-target lesions with or without the appearance of new lesion.

**Table 6. Classification of responses**

Target lesions	Nontarget lesions	New lesions	Overall response
CR	CR/NA	No	CR
CR	SD	No	PR
CR	UE/ND	No	UE
PR	Non-PD/NA	No	PR
PR	UE/ND	No	UE
SD	Non-PD/NA	No	SD
SD	UE/ND	No	UE
PD	Any	Yes or no*	PD
Any	PD	Yes or no*	PD
Any	Any	Yes*	PD
UE	Non-PD/NA	No	UE
ND	Non-PD/NA	No	UE
NA	SD	No	SD
NA	CR	No	CR

CR: complete response; PR: partial response SD: stable disease; PD: progressive response; UE: unable to evaluate (any target or non-target lesion present at baseline which was not assessed or unable to be evaluated leading to an inability to = determine the status of that particular tumor for that time point); NA: not applicable;(no target or nontarget lesions identified at baseline); ND: not done (scans not performed at this timepoint)

Patients with a global deterioration of health status requiring discontinuation of treatment without objective evidence of disease progression at that time are to be classified as having “symptomatic deterioration.”

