#### **4.3. Exclusion criteria**

- Patients with large centrally located pulmonary lesions adjacent to or invading large blood vessels.
- Hemoptysis more than  $\frac{1}{2}$  teaspoon (approximately 2-3 mL) of red blood per day.
- Patients who still have  $\geq$  grade 2 toxicities from prior therapies.
- Concurrent unstable or uncontrolled medical conditions with either of the followings:
  - Active systemic infections;
  - Poorly controlled hypertension (systolic blood pressure  $\geq$  160 mmHg or diastolic blood pressure  $\geq$ 100 mmHg), or poor compliance with anti-hypertensive agents;
  - Clinically significant arrhythmia, unstable angina pectoris, congestive heart failure (class III or IV of New York Heart Association [NYHA]) or acute myocardial infarction within 6 months;
  - Uncontrolled diabetes or poor compliance with hypoglycemics;
  - The presence of chronically unhealed wound or ulcers
  - Other chronic diseases, which, in the opinion of the investigator, could compromise safety of the patient or the integrity of study.
- Newly-diagnosed or symptomatic brain metastases (patients with a history of brain metastases must have received definitive surgery or radiotherapy, be clinically stable, and not taking steroids for brain edema). Anticonvulsants are allowed.
- Any concurrent malignancy other than basal cell carcinoma or carcinoma in situ of the cervix. (Patients with a previous malignancy but without evidence of disease for  $\geq$  3 years are allowed to participate).
- Pregnancy (confirmed by serum beta human chorionic gonadotropin [ $\beta$ HCG]) or breast-feeding (for female patients only).
- A known history or clinical evidence of a deep vein or arterial thrombosis, or pulmonary embolism within 6 months of first infusion of HLX06.
- Less than six weeks from last infusion of ramucirumab, or any other anti-VEGF monoclonal antibody therapy (Last treatment with other monoclonal antibodies targeting proteins other than anti-angiogenic factors is permitted if  $\geq$  4 weeks prior to the first infusion of HLX06).

- Proteinuria  $\geq 2+$  in routine urinalysis (patients with a protein value of  $\leq 500$  mg confirmed by a 24-hour urine collection are eligible).
- Known history of human immunodeficiency virus infection (HIV).
- The patient is the investigator, sub-investigator or any one directly involved in the conduct of the study.

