 If all patients should have confirmed pathologic diagnosis, if not, a pathology review might be necessary.

 If no prior record of pathologic diagnosis is available, a tumor biopsy is required.

 PSA is needed for patients with prostate cancer.

 Postmenopausal women must be amenorrheic for at least 12 months in order not to be considered of child-bearing potential.

22. Urinalysis.
23. Chest radiograph (X-ray)
24. 12-lead electrocardiogram (ECG).
25. Tumor imaging with contrasted computerized tomography or MRI (chest, abdomen and pelvis) for tumor assessment (if the imaging studies are less than 6 weeks before 1st infusion of IP, no need to repeat the studies).
26. Contrast brain CT/MRI (if the imaging studies are less than 8 weeks before 1st infusion of HLX06, no need to repeat the test).
27. Cardiac ultrasound or a MUGA scan
28. Bone scan (if signs or symptoms suggestive of bone metastases are present).  
Confirmative X-ray, CT or MRI for bone metastases for patients with positive bone scan. *The selection of imaging modality is based on the discretion of investigators for the benefit of patients.*
29. Concomitant medications including alternative medicines.
30. Assessment of adverse events from prior therapies.

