Immunogenicity study 		X	X	X	X	X								X
Optional PD study 		X	X	X	X									
Imaging procedures														
12-lead ECG 	X	X				X				x				X
Cardiac ultrasound	X													
Chest X-Ray	X													
Tumor assessment CT/MRI imaging	X	Every 8 weeks in the first 24 weeks and every 12 weeks thereafter												X
Brain CT/MRI	X													
Bone scan	X	Repeat bone scan for metastatic bone disease is indicated based on clinical judgement by the Investigator												

 Pharmacokinetic analysis of HLX06: blood samples of 5 mL were drawn within one hour before and at the end of infusion, 2, 4, 8 ( $\pm 15$  minutes allowable) hours as well as at 24, 48, 96, and 168 hours after the start of 1st and 4th infusion in Cycle 1. Additional time points include before and after 2nd and 3rd infusions in Cycle 1. Thereafter, the serum levels of HLX06 will be measured before the first infusion of Cycle 2 to Cycle 6 or up to 24 weeks, whichever comes first; and on the day follow-up visit 1, whenever possible.

 Blood samples for immunogenicity will be collected from all patients prior to every infusion of IP in Cycle 1 and before first infusion in subsequent 5 cycles or up to 18 weeks, whichever comes first; and on the day of follow-up visit 1.

 The sampling time points are predose and after each infusion (within 30 minutes) in cycle 1 in conjunction with pharmacokinetic studies.

 At screening, predose and after the end of 1st infusion (within 30 minutes) of each cycle and on the day of follow-up visit 1.

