**Table 7. Definition of lesions and imaging modality and their requirement**

Definitions	Description
Measurable lesions	Target lesions that can be measured accurately in at least one dimension (longest diameter to be recorded) as $\geq 20$ mm with conventional techniques, or as $\geq 10$ mm with spiral (helical) computed tomography (CT) scan or two (2) times the reconstruction interval (RI) when using spiral (helical) or multidetector CT, but not less than 10 mm.
Non-measurable lesions	Non-target lesions not classified as measurable lesions (longest diameter $<20$ mm with conventional techniques or $<10$ mm with spiral CT scan) and truly non-measurable lesions. These include bone lesions on BS, effusions, and leptomeningeal disease. Any measurable lesions that were not classified as target lesions will be classified as non-target lesions.
Target lesions	
All measurable lesions up to a maximum of 5 lesions and 2 lesions per organ, representative of all involved organs, are to be identified as target lesions and recorded and measured. Target lesions are to be selected on the basis of their size (those with the longest diameter) and their suitability for accurate repeated measurements (either by imaging techniques or clinically).
 
All lesions other than target lesions (or sites of disease) are to be identified as nontarget lesions and are to be recorded. Measurements of these lesions are not required, but the presence or absence of each is to be noted.

Definitions	Description
	
Longest diameter for target lesions - The sum of the longest diameter for all target lesions (SLD).
 
Complete response - Disappearance of all target lesions.
 
Partial response: At least a 30% decrease in the sum of the longest diameter of target lesions, taking as reference the Screening sum longest diameter.
 
Stable disease: Neither sufficient shrinkage to qualify for partial response nor sufficient increase to qualify for progressive disease.
 
Progressive disease: At least a 20% increase in the sum of the longest diameters of target lesions (with addition of diameters of any newly emergent measurable lesions), taking as reference the smallest sum of the longest diameters (nadir) recorded since screening.
 
UE/ND/NA

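### Table 6 makes the overall response not evaluable when a non-target lesion is not re-imaged, yet Section 14 marks brain imaging at screening only and leaves repeat bone scans optional

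*Combined protocol and SAP*

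**What the plan says.** **Response rule.** Table 6 in Section 15.4 has three rows in which the non-target entry is UE/ND and there is no new lesion. They pair it with target CR, PR and SD, and all three give an overall response of UE. The footnote defines UE as "any target or non-target lesion present at baseline which was not assessed or unable to be evaluated", with the condition that this leaves the status of that tumor undetermined at the time point. ND has its own definition: "ND: not done (scans not performed at this timepoint".

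**What is a non-target lesion.** Section 15.4, Documentation of Target and Non-Target Lesions: "All other lesions (or sites of disease) should be identified as non-target lesions and should be recorded at baseline". Table 7 places bone-scan lesions among the truly non-measurable ones: "These include bone lesions on BS, effusions, and leptomeningeal disease".

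**Eligibility.** Section 4.3 excludes new or symptomatic brain metastases but admits treated ones: "patients with a history of brain metastases must have received definitive surgery or radiotherapy, be clinically stable". Section 4 does not exclude bone metastases.

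**Schedule.** In Section 14 the brain CT/MRI row is marked at screening and nowhere else. For bone: "Repeat bone scan for metastatic bone disease is indicated based on clinical judgement by the Investigator". Even the baseline scan is conditional in Section 7.1.1: "Bone scan (if signs or symptoms suggestive of bone metastases are present". Tumor CT/MRI is repeated at 8-week intervals up to week 24 and 12-week intervals after that. Section 7.1.1 gives its region as chest, abdomen and pelvis and lists the brain separately.

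**Text pulling the other way.** Section 15.4 wants the status of each non-target lesion recorded throughout follow-up. Table 7 requires one modality per recorded lesion for the whole study, and Section 8.3 asks for the same modalities at efficacy evaluation.

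**The concern.** The response rule assumes that every recorded non-target site is looked at each time. The schedule does not provide for that in the brain, or for bone disease outside the body CT/MRI field. A site that follows Section 14 exactly can therefore produce an overall response of UE for a patient whose target disease is shrinking or stable.

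ORR, DCR and duration of response are listed secondary endpoints (Section 3.6). Patients who are only ever UE stay in the ORR and DCR denominators as failures, so both rates are pulled down. They also never enter duration of response, which is summarized for confirmed responders only.

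The effect is not symmetric. PD is reachable from any imaging that shows it, whereas CR, PR or SD requires a scan that the schedule does not ask for. In an open-label study, whether an affected patient can count as a responder then depends on whether the investigator chose to order that scan.

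**Working it through.** The plan sizes no efficacy hypothesis and states no ORR or DCR that depends on this rule, so there is no figure to reproduce. The check sets the texts side by side and then puts a bound on the effect.

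**1. The rule.** Table 6 has 14 rows. Those with a non-target entry of UE/ND are:

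| Target | Non-target | New lesion | Overall |
|---|---|---|---|
| CR | UE/ND | No | UE |
| PR | UE/ND | No | UE |
| SD | UE/ND | No | UE |

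No row covers target NA with non-target UE/ND. Section 4.2 admits patients with evaluable but not measurable disease, so that combination can arise and has no stated outcome.

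**2. One patient traced through the schedule.** A treated, stable brain metastasis leaves a residual lesion, recorded as non-target at baseline. At week 8 the scheduled CT/MRI of chest, abdomen and pelvis shows the target sum down by 50% and no new lesion. The brain is not scanned, so that lesion is ND. Table 6 gives PR + UE/ND = UE. The same happens at weeks 16, 24, 36 and so on. The only other outcome this patient can reach is PD.

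**3. Who is not affected.** A bone lesion visible on the scheduled CT/MRI can be assessed there. A patient whose investigator orders the optional scans can also be classified. For CR or PR, though, Section 15.4 requires confirmation at a repeat assessment at least 28 days later, so the non-target site must be assessable at both visits and a single optional scan is not enough.

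**4. Denominators.**
- ORR (Sections 8.3 and 11.3.4): treated patients with measurable disease at baseline.
- DCR (Section 8.3): all treated patients.
- DCR (Section 11.3.4): treated patients with measurable disease at baseline.

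None of these drops a UE patient who has measurable disease.

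**5. Bound on DCR.** Let k be the number of treated patients who are UE at every assessment. The documents do not give k; the values below are assumed. With the maximum of 30 treated patients (Section 4.1) and the Section 8.3 denominator,

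highest possible DCR = (30 − k)/30.

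| k (assumed) | Calculation | Ceiling on DCR |
|---|---|---|
| 0 | 30/30 | 100% |
| 1 | 29/30 | 96.7% |
| 3 | 27/30 | 90% |
| 6 | 24/30 | 80% |

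The same ceiling applies to ORR, and to DCR as defined in Section 11.3.4, if all 30 have measurable disease. With fewer measurable patients, 30 is replaced by their number and k by the affected patients among them.

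**6. What the existing rows imply for an unseen lesion.** If the unimaged non-target lesion has not progressed, it is either CR or SD. Existing rows then give CR or PR for target CR, PR for target PR, and SD for target SD. The lower bounds are PR, PR and SD.

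**The case against.** The strongest reply is that the documents do require recorded lesions to be followed. Section 15.4 asks for the status of each non-target lesion throughout follow-up, Table 7 requires the same modality throughout, and Section 8.3 repeats this. A site that obeyed those passages would re-scan the brain and bone lesions, and UE would not arise. That stands as far as it goes, and it makes the finding a conflict between passages. It does not remove the problem, because Section 14 does not schedule what those passages require, and Section 8.3 makes the bone scan discretionary in the sentence after it asks for the same modalities.

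The UE definition also applies only where the missed assessment prevents a lesion's status from being determined. That is correct, but the rows read UE/ND, and ND carries no such condition.

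On-study brain imaging is not ruled out. The repeated tumor CT/MRI row in Section 14 names no body region, and Section 6.2 foresees new CNS metastases found at a later imaging assessment. This is fair, but the only stated region is chest, abdomen and pelvis, and brain imaging has its own row marked at screening only.

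The affected group is also limited. A fully resected brain metastasis may leave nothing to record, and hepatocellular carcinoma is assessed by mRECIST (Synopsis, Treatment evaluation), so Table 6 may not govern those patients. Efficacy here is descriptive, and individual tumor measurements will be listed, so target shrinkage stays visible. All of this stands and limits the weight of the point.

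A reader might infer that no patient with brain or bone metastases can ever count as CR, PR or SD. The documents do not support that: optional scans are allowed, and many bone lesions may lie within the scheduled field.

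**Conclusion.** Section 14 and Table 6 conflict. For a patient with a residual treated brain lesion, or a bone lesion outside the scheduled CT/MRI field, recorded as non-target and imaged only as scheduled, every overall response is UE or PD, and the patient counts as a failure in ORR and DCR. For that group the two rates are biased downward, and the result depends on discretionary scanning. The point should be settled before responses are classified. It does not touch the MTD or the safety endpoints.

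The size cannot be derived from the documents. The ceiling of (30 − k)/30 is an illustration: 90% at k = 3 and 80% at k = 6. It assumes that 30 patients are treated and that the k patients are UE throughout.

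A reader might go further and say that a DCR of 60% would be reported as 48% if 20% of patients were affected (0.60 × 0.80). The documents do not support that as an estimate. The 60% in Section 1.3.2 is a stable-disease rate for ramucirumab, the 20% has no source, and the product assumes that being unscanned is unrelated to response. That last assumption is doubtful when scans are ordered on clinical judgement.

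**What to change.** 1. In Table 6, change three rows to CR + UE/ND = PR, PR + UE/ND = PR and SD + UE/ND = SD. Apply them only where the sole gap is a non-target site that was not imaged, there is no new lesion, and no non-target progression appears on the imaging or clinical assessment that was done.
2. Keep UE whenever a target lesion was not assessed.
3. Add a row: target NA with non-target UE/ND = UE.
4. Reconcile Section 14 with Section 8.3, the non-target follow-up text in Section 15.4 and the same-modality requirement in Table 7, so that it is clear how a recorded brain or bone lesion is assessed at each time point.
5. Report how many CR, PR and SD classifications rest on an unassessed non-target site, and show ORR and DCR again with those patients classed as UE.

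The cost is three edited rows, one new row, a wording reconciliation and one extra tabulation. The row changes need no additional scans. The downside is real: under the present rows a patient with unseen brain or bone progression is UE, whereas under the new rows that patient could be counted as PR or SD. The sensitivity analysis in item 5 is there to show how far the results depend on this, so it should be adopted together with the row changes.

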**Table 7. Definition of lesions and imaging modality and their requirement**

Definitions	Description
Measurable lesions	Target lesions that can be measured accurately in at least one dimension (longest diameter to be recorded) as $\geq 20$ mm with conventional techniques, or as $\geq 10$ mm with spiral (helical) computed tomography (CT) scan or two (2) times the reconstruction interval (RI) when using spiral (helical) or multidetector CT, but not less than 10 mm.
Non-measurable lesions	Non-target lesions not classified as measurable lesions (longest diameter $<20$ mm with conventional techniques or $<10$ mm with spiral CT scan) and truly non-measurable lesions. These include bone lesions on BS, effusions, and leptomeningeal disease. Any measurable lesions that were not classified as target lesions will be classified as non-target lesions.
Target lesions	
All measurable lesions up to a maximum of 5 lesions and 2 lesions per organ, representative of all involved organs, are to be identified as target lesions and recorded and measured. Target lesions are to be selected on the basis of their size (those with the longest diameter) and their suitability for accurate repeated measurements (either by imaging techniques or clinically).
 
All lesions other than target lesions (or sites of disease) are to be identified as nontarget lesions and are to be recorded. Measurements of these lesions are not required, but the presence or absence of each is to be noted.

Definitions	Description
	
Longest diameter for target lesions - The sum of the longest diameter for all target lesions (SLD).
 
Complete response - Disappearance of all target lesions.
 
Partial response: At least a 30% decrease in the sum of the longest diameter of target lesions, taking as reference the Screening sum longest diameter.
 
Stable disease: Neither sufficient shrinkage to qualify for partial response nor sufficient increase to qualify for progressive disease.
 
Progressive disease: At least a 20% increase in the sum of the longest diameters of target lesions (with addition of diameters of any newly emergent measurable lesions), taking as reference the smallest sum of the longest diameters (nadir) recorded since screening.
 
UE/ND/NA

Non-target lesions	
All lesions other than target lesions (or sites of disease) are to be identified as nontarget lesions and are to be recorded. Measurements of these lesions are not required, but the presence or absence of each is to be noted.
 
Complete response: Disappearance of all non-target lesions.
 
Incomplete response/stable disease: Persistence of one or more non-target lesion(s).
 
Progressive disease: Unequivocal progression of a non-target lesion or appearance of 1 or more new lesions.

Definitions	Description
	UE/ND/NA
Best overall response	The best overall response is the confirmed overall response. To be assigned a best overall response of partial response or complete response, change in tumor measurements must be confirmed by repeat assessment no less than 4 weeks after the criteria for response of CR or PR are first met.
Methods of measurements	The same imaging modality, method of assessment, and technique must be used throughout the study to characterize each identified and reported lesion.  All measurements are to be made with a ruler or calipers; measurements are to be recorded in metric notation.
Clinical examination	Clinically detected lesions are only to be considered measurable when they are superficial (e.g., skin nodules and palpable lymph nodes). For skin lesions, documentation by color photography—including a ruler to estimate the size of the lesion—is recommended.
Chest X-ray	Lesions on the chest X-ray are to be acceptable as measurable lesions when they are clearly defined and surrounded by aerated lung. Chest X ray is to be performed in full inspiration in the poster-anterior projection. The film to tube distance is to remain constant between examinations. If patients with advanced disease are not well enough to fulfill these criteria, such situations are to be reported together with the measurements. Lesions bordering the thoracic wall, and lesions bordering or

Definitions	Description
	involving the mediastinum, are not suitable for measurements by chest x-ray.
Computed Tomography and Magnetic Resonance Imaging	
CT is the primary imaging modality of choice. Conventional CT and magnetic resonance imaging (MRI) are to be performed with contiguous cuts of 10 mm or less in slice thickness. Spiral CT is to be performed by use of a 5mm contiguous reconstruction algorithm. CT scans of the thorax, abdomen, and pelvis are to be contiguous throughout the anatomic region of interest. The minimum size of the lesion is to be no less than double the slice thickness.
 
The longest diameter of each target lesion is to be selected in the axial plane only. For spiral CT scanners, the minimum size of any given lesion at Screening may be 10 mm, provided the images are reconstructed contiguously at 5 mm intervals.
 
For conventional CT scanners, the minimum-sized lesion is to be 20 mm by use of a contiguous slice thickness of 10 mm.
 
In patients in whom the abdomen and pelvis have been imaged, oral contrast agents are to be given to accentuate the bowel against other soft-tissue masses. Intravenous contrast agents are also to be given, unless contraindicated for medical reasons such as allergy. An adequate volume of a suitable contrast agent is to be given so that the metastases are demonstrated the best effect. All images from each examination are to be included and not “selected” images of the apparent lesion.

Definitions	Description
	
All window settings are to be included, particularly in the thorax, where the lung and soft-tissue windows are to be considered. Lesions are to be measured on the same window setting on each examination.
 
When MRI is used, lesions are to be measured in the same anatomic plane by use of the same imaging sequences on subsequent examinations. Wherever possible, the same scanner is to be used.

Bone scan	Bone scans are to be used for the assessment of non-target lesions only.
Ultrasound	Ultrasound is not to be used to measure tumor lesions that are clinically not easily accessible.

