#### **11.3.4. Efficacy**

The primary efficacy parameter is the objective response rate: (ORR, number of subjects with confirmed responses of CR or PR), divided by the total number of treated subjects with measurable disease at baseline). Tumor response status will be defined according to RECIST 1.1 (Appendix 15.4). To perform an evaluation of anti-tumor activity, BOR outcomes, ORR, and disease control rate (DCR: number of patients with CR, PR, or SD divided by the total number of treated patients with measurable disease at baseline) will be tabulated by overall frequency distribution. Median time to response and duration of response will be summarized for those subjects with confirmed responses, using Kaplan-Meier methods; PFS will be similarly summarized. Listings of individual tumor measurements, tumor burden and % changes in tumor burden will be provided. Changes in tumor burden will be presented graphically for each disease type, e.g. by waterfall or other plots.

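### Appendix 15.4 has no lymph-node rule: a node that shrinks to normal size but stays visible blocks complete response, and a static target node dilutes change in the lesion sum

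*Combined protocol and SAP*

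**What the plan says.** Section 11.3.4 fixes the standard and where it is written down: "Tumor response status will be defined according to RECIST 1.1 (Appendix 15.4". The appendix is therefore the text a site reader will apply.

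Appendix 15.4 treats every lesion alike:

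- **Dimension.** Table 7 records the longest diameter for measurable lesions ("Target lesions that can be measured accurately in at least one dimension (longest diameter to be recorded"). Its CT/MRI row adds: "The longest diameter of each target lesion is to be selected in the axial plane only". The text before Table 6 sums these diameters into the SLD.
- **Minimum size.** "For spiral CT scanners, the minimum size of any given lesion at Screening may be 10 mm". The conventional-CT minimum is 20 mm. Smaller lesions are non-measurable and so non-target, with no lower floor.
- **Target selection.** "Target lesions are to be selected on the basis of their size (those with the longest diameter".
- **Complete response.** The non-target rule is "Disappearance of all non-target lesions", and the target rule has the same form. A non-target lesion that is still present counts as incomplete response or SD.
- **Combination.** Table 6 turns target CR with non-target SD into an overall PR.
- **Lymph nodes.** They appear once, in the clinical-examination row: "Clinically detected lesions are only to be considered measurable when they are superficial (e.g., skin nodules and palpable lymph nodes".

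Neither the appendix nor the body of the protocol gives a nodal axis, a nodal size limit or a definition of CR for a node.

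**The concern.** A lymph node is a normal structure. Successful treatment can leave it in place at normal size. A rule that recognises only disappearance has no category for that outcome, so the literal text scores the node as residual disease.

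Two consequences follow. First, a patient whose other disease has gone can be recorded as PR because a node is still visible. Second, if a node that is no longer disease (or never was) sits in the target sum, it adds a constant to both the baseline and the follow-up sum. That pulls every percentage change towards zero, so PR is harder to reach and progression is called later.

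Section 11.3.4 names ORR as the main efficacy parameter and also reports best overall response, response duration and PFS. All of these rest on the appendix rules.

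**Working it through.** The plan states no expected response rate or power for tumor response, so there is no figure to reproduce. The check applies the appendix's own thresholds to assumed lesion sizes.

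**Inputs from Table 7.** PR is a fall of 30% or more in the SLD from baseline. Progression (PD) is a rise of 20% or more from the smallest SLD.

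**Assumptions, not in the documents.** Tumor sum T; k static nodes recorded as targets, each of longest diameter L. The documents do not say what size a normal node is.

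**1. CR blocked.** Take T = 20 mm and one 12 mm node. The tumor vanishes and the node stays. The SLD goes from 32 to 12 mm, a fall of 20/32 = 62.5%. The node has not disappeared, so the result is PR. The non-target route ends in the same place: target CR plus a visible non-target node is PR under Table 6.

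**2. Shrinkage diluted.** If the tumor shrinks 40% and a 12 mm node is static, the SLD falls by 0.4T/(T + 12).

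| T (mm) | SLD fall | Category |
|---|---|---|
| 20 | 8/32 = 25.0% | SD |
| 36 | 14.4/48 = 30.0% | PR (boundary) |
| 50 | 20/62 = 32.3% | PR |
| 80 | 32/92 = 34.8% | PR |

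The switch point solves 0.4T = 0.3(T + 12), which gives T = 36 mm. Below it, a 40% shrinkage reads as SD.

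**3. Growth diluted.** With the nadir at baseline, PD needs true tumor growth of 0.20(T + kL)/T. For T = 20 mm and one 12 mm node this is 0.20 × 32/20 = 32%, against 20% without the node. The matching PR requirement is 0.30 × 32/20 = 48%, against 30%.

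**4. Range.** Over T = 20 to 100 mm, k = 1 or 2 and L = 10 to 15 mm:

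- PR needs a true tumor shrinkage of 33.0% (T = 100, one 10 mm node) to 75.0% (T = 20, two 15 mm nodes).
- PD needs a true growth of 22.0% to 50.0% over the same two extremes.
- If all true tumor vanishes, the SLD falls by T/(T + kL), which is 40.0% to 90.9%. This always meets the PR threshold.

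**5. Which endpoints move.**

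- CR to PR: best overall response only. ORR pools CR and PR, so it is unchanged.
- PR to SD: ORR. With 30 evaluable patients, one such shift is 1/30 = 3.3 points. The actual denominator is treated patients with measurable disease, so the figure is approximate.
- Disease control rate: unchanged by either shift, because it counts CR, PR and SD together.
- Later PD: can affect PFS and response duration.

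**The case against.** The strongest reply is that the appendix speaks of lesions and sites of disease, not of anatomy. Nothing tells a reader to record a healthy node, and selecting the largest lesions first, with a cap, works against small nodes. This stands. A reader might infer that normal-sized nodes enter the target sum as a matter of course, or that a patient with only a healthy node joins the ORR denominator. The documents do not support either reading. A node can be recorded as a target under the longest-diameter rule, but need not be. If a static node is still diseased, keeping it in the sum is correct.

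A reader might also infer that CR is unattainable with nodal disease. That goes too far, since CR remains open when the node can no longer be seen. Nor does every reclassified patient move ORR by 3.3 points; CR-to-PR shifts move it by nothing. The bias is also not only against response, because the same dilution delays progression.

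It can further be said that naming RECIST 1.1 is enough, since trained readers will apply the published guideline. That may happen in practice, but Section 11.3.4 points to the appendix as the definition. What the guideline (reference 25) says about nodes cannot be checked from these documents, so this point rests on the appendix's own text.

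Finally, this is a first-in-human dose-finding study. Its primary outcomes are adverse events and the MTD, and response is tabulated without a hypothesis or decision rule. Hepatocellular carcinoma is assessed by mRECIST under the Synopsis footnote. Both facts lower the priority of the point but leave the rule as it is.

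**Conclusion.** The concern holds in a limited form. Appendix 15.4 applies one longest-diameter rule, one spiral-CT minimum and one disappearance rule to all lesions, admits palpable nodes as measurable, and says nothing about how to measure or clear a node. On its literal text, a nodal lesion that is normal in size but still visible caps the patient at PR. That conclusion needs only the appendix wording and the premise that a treated node can stay visible.

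The dilution effect depends on assumed sizes and on a node that is not disease being recorded as a target. In the illustration with a 12 mm node and 40% tumor shrinkage, the category changes only for tumor sums below 36 mm. The effect is confined to best overall response, ORR, response duration and PFS in patients with nodal lesions assessed by Appendix 15.4. Dose finding is unaffected. It is a low-priority correction, but a specific one.

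**What to change.** Add a lymph-node rule to Appendix 15.4, with thresholds taken from the RECIST 1.1 guideline the plan already cites (reference 25):

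- Measure nodes by short axis, and enter that value in the sum in place of the longest diameter.
- State the short-axis size at which a node may be a target, the range in which it is non-target, and the size below which it is normal and not recorded as a lesion.
- Define CR as disappearance of all non-nodal lesions with every node below the normal-size limit. Apply this to both the target and the non-target rows of Table 7.
- Note that the sum need not be zero at CR when a target node remains visible at normal size.

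The cost is appendix wording. Sites read the same scans, and no imaging is added.
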